### 5.2. Instrumental Variable (IV) Analysis

Participants are considered to have adhered to the intervention if they received both a completion certificate and seed capital.

Two-stage least squares (2SLS) using `ivregress 2sls` in Stata.

Stage 1: Predict adherence using treatment assignment as an instrument.

Stage 2: Estimate the causal effect of adherence on outcome changes.

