## 3. Study Sample

Participants were randomized within each of three cities to the treatment or control group. Inclusion was restricted to women scoring between 2.0 and 4.25 on the SRI at baseline. Additional inclusion criteria included: being a woman at least 18 years of age; at risk of or had ever experienced gender-based violence; Colombian or Venezuelan (with a Temporary Protection Permit); resided in Colombia for at least six months; and had an entrepreneur profile assessed through HIAS' profile scanning process.

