## 4. Descriptive and Baseline Analysis

- Baseline Balance: Descriptive statistics will be computed separately by study arm. Mean comparisons will be conducted using independent samples t-tests.
- Imbalance Adjustment: Outcomes found to differ significantly at baseline between groups will be included as controls in regression models of change scores.

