## 5. Estimating Treatment Effects

### 5.1. Intent-to-Treat (ITT) Analysis

OLS regression models will estimate the average treatment effect of assignment to the treatment group on changes in each outcome.

Models:

1. Bivariate association between treatment assignment and outcome change.
2. Model 1 + controls for baseline value of outcome.
3. Model 2 + controls for baseline covariates associated with outcome of interest at baseline.

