## 7. Sensitivity Analyses

Compare results using:

- Change scores vs. endline-only models controlling for baseline values.

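### The 2SLS covariates are not stated and no model names city, the randomisation stratum, so the LATE interval may be wider than the data allow

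*SAP*

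**What the plan says.** SAP section 1 makes the LATE a stated objective alongside the ITT effect. Section 5.2 defines adherence, names the Stata 2SLS command, and gives the stages: "Stage 1: Predict adherence using treatment assignment as an instrument" and "Stage 2: Estimate the causal effect of adherence on outcome changes". It lists no covariates and does not say whether the three ITT models carry over.

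Those ITT models, in section 5.1, are:

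- Model 1: "Bivariate association between treatment assignment and outcome change"
- Model 2: "Model 1 + controls for baseline value of outcome"
- Model 3: "Model 2 + controls for baseline covariates associated with outcome of interest at baseline"

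Three other passages bear on the point:

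- **Stratum.** Section 3 says "Participants were randomized within each of three cities to the treatment or control group". The Protocol (Subject Recruitment, enrolment and sample size) plans 80 women per city at 2:1, but in four cities. The SAP states no ratio.
- **Imbalance rule.** Section 4 says "Outcomes found to differ significantly at baseline between groups will be included as controls in regression models of change scores".
- **Sensitivity analysis.** Section 7 plans a comparison of "Change scores vs. endline-only models controlling for baseline values", without saying whether this includes the 2SLS.

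The Protocol's covariate sentence (Quantitative data analysis) concerns its random coefficient models and does not name city.

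**The concern.** With one binary instrument and no covariates, 2SLS reduces to the Model 1 ITT coefficient divided by the difference in adherence between arms. The LATE then lacks the baseline adjustment that the SAP already plans for the ITT effect, although both use the same participants and the same change scores. If the baseline score predicts change, its residual variance goes into the LATE interval for no reason.

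The smaller part of the gap is city. Participants were randomised within city, yet city can enter a model only through ITT Model 3, and only if it happens to be associated with the outcome at baseline. If city predicts change, the reported standard errors ignore the stratification.

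At stake is the precision of a stated estimand, and whether its specification is fixed in advance or chosen at analysis.

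**Working it through.** The documents give no precision figure to reproduce: no test level, power, SD, correlation or adherence rate is stated. The inputs below are assumptions, apart from 80 per city and 2:1 (Protocol) and three cities (SAP). Tests are taken as two-sided at 5%.

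**1. Baseline outcome left out.** Let *r* be the baseline-endline correlation and *k* the baseline SD divided by the endline SD. In units of the endline variance, the change score has variance 1 + k² − 2rk. After adjustment for baseline the residual variance is 1 − r². Adherence and sample size cancel, so the ratio of LATE standard errors, unadjusted to adjusted, is

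sqrt[(1 + k² − 2rk) / (1 − r²)].

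Example, k = 1 and r = 0.5: sqrt(1 / 0.75) = 1.155.

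| k | r = 0.3 | r = 0.5 | r = 0.7 |
|---|---|---|---|
| 1 | 1.240 | 1.155 | 1.085 |
| 0.85 | 1.154 | 1.079 | 1.022 |
| 0.7 | 1.084 | 1.026 | 1.000 |

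At k = 1 and r = 0.5 the variance ratio is 1 / 0.75, so the unadjusted analysis is worth three quarters of the sample. In absolute terms, with 240 women (160 and 80) and 80% adherence, the LATE half-width is 1.96 × sqrt(1/160 + 1/80) / 0.8 = 0.335 SD unadjusted. Adjusted, it is 0.335 × sqrt(0.75), about 0.29 SD.

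Simulated 2SLS (1,500 null trials per cell, n = 240 and 320, adherence 70% and 90%) gave mean reported SE ratios of 1.24/1.15/1.08 at k = 1, 1.15/1.08/1.02 at k = 0.85 and 1.08/1.03/1.00 at k = 0.7.

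**2. Does the section 4 imbalance rule rescue this?** It reaches regressions of change scores, so on its plain words it covers stage 2. But it acts only after a significant baseline difference, which sound randomisation produces about 5% of the time. In simulation it acted in 3.7% to 6.2% of trials per cell. The mean reported SE was still 22–23%, 15% and 8% larger at k = 1. It cannot bring in city.

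**3. City left out, same ratio in every city.** If city explains a share R² of the variance in change, the reported SE is too large by 1/sqrt(1 − R²) − 1. With fixed counts per city, the type I error is 2 × [1 − Φ(1.96 / sqrt(1 − R²))].

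| R² | Excess in reported SE | Type I error |
|---|---|---|
| 0 | 0% | 5.0% |
| 1% | 0.5% | 4.9% |
| 2% | 1.0% | 4.8% |
| 5% | 2.6% | 4.4% |
| 10% | 5.4% | 3.9% |

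Simulation (4,000 null trials per cell, 3 × 80, 53 of 80 treated in each city, 70% adherence) confirmed that with fixed counts the actual spread of the estimate is the same with and without city: 0.192, 0.192 and 0.184 at R² of 2%, 5% and 10%. Only the reported SE changes. Under simple randomisation within city there is a small real loss.

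**4. Both together.** With 3 × 80, r = 0.5, R² = 10% and 80% adherence, the mean 95% interval width in baseline-SD units was 0.704 with no covariates, 0.664 with city, 0.619 with baseline and 0.575 with both. The interval without covariates is 0.704 / 0.575 = 1.22 times as wide. The actual spread was 0.165 against 0.145, a ratio of 1.14; the rest is overstatement of the SE.

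**5. If treatment shares differed by city.** No passage says they did. In the worst direction, with 70% adherence and assumed shares of 60/66/73%, the unadjusted LATE bias was 0.05, 0.08 and 0.10 SD of change at R² of 2%, 5% and 10%, with 5–7% rejection under the null. With city terms the bias was about zero and rejection 4.6–5.5% in all the unequal-share cells run.

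**The case against.** The strongest reply is that silence is not exclusion. Section 5.2 is a short outline placed directly after Models 1 to 3, and carrying those models into the 2SLS is a natural reading. If section 7 covers the 2SLS, a baseline-adjusted LATE is already planned, because change adjusted for baseline and endline adjusted for baseline give the same treatment coefficient. That is fair, and it limits the criticism to an unstated specification. But neither section says so, and neither reading brings in city.

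Second, little information is lost. With one instrument, the adjusted LATE is the Model 2 coefficient divided by the adjusted adherence difference, so a reader could approximate it from planned output. Model 2 also already tests the same null with baseline adjustment. This stands: the cost falls on the LATE interval, and power is not lost to the same extent.

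Third, the 24% figure is least apt for the SRI. Eligibility truncates the baseline SRI (2.0 to 4.25 in the SAP, 2 to 3.5 in the Protocol), which reduces its SD. Suppose the SDs were equal before selection and truncation cut the baseline SD to 0.7 of its unselected value. The ratio becomes sqrt[1 + 0.49(1 − r)² / (1 − r²)], an excess of 12%, 8% and 4% at unselected correlations of 0.3, 0.5 and 0.7. This also stands. PHQ-9 and BRCS are not truncated in this way.

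Finally, the unequal-share scenario is hypothetical, since the Protocol plans 2:1 in every city. It is a reason to state the ratio, not evidence of bias.

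**Conclusion.** The concern holds as a minor one. The 2SLS covariates are unstated and no model names city. Followed literally, the LATE standard error is 0% to 24% larger than with baseline adjustment, over correlations of 0.3 to 0.7 and SD ratios of 0.7 to 1. Omitting city costs less and possibly nothing: about 1% to 5% in the reported SE at R² of 2% to 10%, in the conservative direction.

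There is no bias and no type I inflation if the ratio was common to all cities. Every magnitude rests on assumed values. As this is a pilot of preliminary effectiveness, the point is a free gain in efficiency and clarity, and validity is not threatened on what the documents say.

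**What to change.** - In SAP section 5.2, state the 2SLS covariates: the baseline value of the outcome and city indicators, in both stages. An unadjusted version can remain as a secondary display.
- In section 5.1, add city indicators to the ITT models.
- In section 7, say whether the comparison applies to the 2SLS.
- In section 3, state the allocation ratio used in each city and whether allocation within city was simple, fixed-count or blocked. Reconcile the SAP's three cities with the Protocol's four before the city terms are written.

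The cost is SAP wording and a few extra terms in existing commands. The 2SLS uses one degree of freedom for baseline and one per city beyond the first: three in all with three cities, four with four. No new data are needed.

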## 6. Handling Attrition

- Attrition Analysis: Logistic regression will assess whether loss to follow-up is associated with baseline characteristics.

## 7. Sensitivity Analyses

Compare results using:

- Change scores vs. endline-only models controlling for baseline values.

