HIAS will promote the incubation of businesses through its Entrepreneurship School with Gender Lens (ESGL), a methodology that targets GBV survivors and women at-risk to help them develop business ideas, access needed support for the prevention of and response to GBV, exploitation and trafficking, and improve participants' overall self-reliance. Participants will go through a general business curriculum, work on business plans and learn gender issues and ways to mitigate GBV risks. Upon training completion, participants are eligible to pitch their business idea to a panel of experts and receive \$800 of seed capital. They will also receive follow-up business advisory support for at least six months, focusing on access to markets and finance and building support networks, in order to continue building self-reliance.

The ESGL will include a mental health and psychosocial support module, contributing to participant self-sufficiency, resilience, and empowerment through skills development such as coping skills, problem-solving capabilities, self-esteem, self-efficacy, communication abilities, self-regulation, and leadership, aimed at strengthening their ability to generate dignified livelihoods.

Study objective

This study will conduct a pilot-randomised controlled trial to evaluate the entrepreneurship curriculum. The evaluation has three primary objectives:

1. Evaluate the preliminary effectiveness of the entrepreneurship programming to improve household self-reliance, mental health, and empowerment for households where women members run businesses.
2. Examine the relationship between GBV risk and self-reliance among women refugees in the Colombian migration context.
3. Assess the feasibility and acceptability of the refugee self-reliance index as a measurement tool in programs that strengthen self-reliance pathways for women individuals.

Methodology

Overview

This pilot RCT will be conducted in Cali, Ipiales, Pasto, and Popayan, and will include a control group. Eligible participants will be randomized to the treatment or control arm and the study team will collect data from both the intervention and comparison groups at: 1) the program baseline, 2) the program endline (8 months post-baseline), and 3) follow-up 3-4 months after program completion.

Screening for Eligibility: Inclusion Criteria

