Participants may feel compelled to consent to the study in spite of the above-mentioned informed consent procedures. Potential power differentials between the participants and data collectors may result in inadvertent coercion to participate in the study. The research team will carefully analyze the context-specific factors that may result in participant coercion and discuss strategies for ensuring genuine informed consent. Some of the measures that may be used include:

- Build on existing staff experience with informed consent procedures in other projects.

- Intensive staff training on the importance of informed consent and procedures to minimize potential coercion. Such procedures may include careful explanation and repetition of the nature of voluntary consent (e.g., participation in the study will not affect access to services; participants are free to refuse to answer any questions or to withdraw from the study at any time). Participants will also be given time to consider their decision.
- Multiple opportunities for participants to ask questions throughout the informed consent process and subsequent data collection. Researchers will be trained to respond to frequently asked questions or concerns that participants may raise. Close collaboration with HIAS staff to avoid recruiting participants who may be unable to provide assent voluntarily due to mental health or cognitive disability.

Data Collection

Participant data will be collected at three time points: baseline (when participants are first enrolled in the study), eight months post-baseline (upon program completion), and three months following endline data collection (eleven months after baseline). Data collectors will be hired and trained by Los Andes and the RSRI team members using a combination of online learning modules and in-person training, which will cover the study tools, evaluation protocol, humanitarian principles and its current practice, safeguarding policies, Psychological First Aid (PFA) gender and GBV, and research ethics and best practice.

Study Outcome Measures and Ascertainment

Self-reliance:

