According to Resolution number 008430 of 1993 of the Colombian Ministry of Health and Social Protection, this is "research without risk", which includes: "studies that employ retrospective documentary research techniques and methods and those in which no intervention or intentional modification of the biological, physiological, psychological or social variables of the individuals participating in the study is carried out, including: review of medical records, interviews, questionnaires and others in which no sensitive aspects of their behaviour are identified or dealt with".

The study is expected to carry minimal risk of loss of confidentiality associated with participation in group discussions, which will be minimized by data confidentiality measures and by using verbal informed consent procedures. Individuals have the option to not participate, or if they choose to participate, to decline to answer any question that they do not feel comfortable answering, or to choose to end their participation in the study at any time. We do not anticipate any psychological risk that may result from study participants. All measures will be taken to minimize the risk related to the contracting and spreading COVID-19 among any of the researchers or study participants, following the guidelines of the Ministry of Health and the University.

Safety and Adverse Events

All referral processes will be handled by HIAS as follows.

CASE MANAGEMENT PROTOCOL AND REFERRAL ROUTES

At HIAS, we have developed clear pathways and procedures to prevent, identify, and promptly address the needs of all Persons of Concern (PDI), that is, all participants who are directly or indirectly involved with each of our programs. For HIAS Colombia, it is essential to meet the needs of our beneficiaries, especially those who will be part of the Owning Rights and Protection: GBV Prevention, Mitigation, and Response in Colombia project.

This protocol was created to specify the pathways for care and management of cases and needs that may arise during the implementation of the research and that, in turn, represent a risk to the psychosocial well-being and safety of our participants and their families. For example, cases of PDI who are not selected to participate in the EGV, participants who have been randomly assigned to the control group, and/or participants who receive EGV training and express some type of need for care.

STEPS FOR CASE MANAGEMENT AND REFERRAL ROUTES

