## 8. Software

All analyses will be conducted in Stata (version 16), using appropriate packages for regression, 2SLS, and multiple imputation.

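### The only listed sensitivity analysis cannot disagree with the adjusted ITT models when participants and covariates are the same, and nothing in the plan tests how loss to follow-up could move the estimates

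*SAP*

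**What the plan says.** SAP section 5.1 fits OLS to the change in each outcome. Model 1 has study arm only. Model 2 is "Model 1 + controls for baseline value of outcome". Model 3 adds further baseline covariates. Section 5.2 gives the 2SLS second stage as "Stage 2: Estimate the causal effect of adherence on outcome changes" and mentions no baseline term.

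Section 7 contains a single comparison: "Change scores vs. endline-only models controlling for baseline values".

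Section 6 is also a single item: "Logistic regression will assess whether loss to follow-up is associated with baseline characteristics". Study arm is not named, and no step feeds into an estimate. The attrition objective in section 1 likewise refers only to participant characteristics. Section 8 says Stata will be used, "using appropriate packages for regression, 2SLS, and multiple imputation"; no other section says what would be imputed or for which analysis.

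Section 4 adds outcomes that are imbalanced at baseline as controls in the change-score models. It does not mention endline models.

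The protocol (Quantitative data analysis) plans random coefficient models over the repeated measurements. The SAP does not carry these forward.

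**The concern.** A sensitivity analysis is useful only if it could have given a different answer. A reader who sees the change-score and baseline-adjusted endline models agree will take that as support for the ITT result, although for Models 2 and 3 the agreement is guaranteed.

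The threat that could move the estimates is loss to follow-up, and the plan does not test it. Retention could differ by arm, because only the treatment arm has training, seed capital and continued contact: "They will also receive follow-up business advisory support for at least six months" (Protocol, Intervention). As written, the plan would not show whether loss differed by arm, or how far outcome-dependent loss could shift the ITT or the LATE.

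**Working it through.** **1. The identity.** Let Y0 be baseline, Y1 endline and T arm.

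- Model 2: Y1 − Y0 = a + bT + cY0 + e.
- Add Y0 to both sides: Y1 = a + bT + (c + 1)Y0 + e, which is the section 7 endline model.

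The residuals are the same, so b, its SE and its p-value are the same. Only the baseline coefficient changes, by exactly 1. Adding the same covariates to both sides gives the same result for Model 3.

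**2. Numerical check.** One simulated 160:80 trial with loss (204 completers):

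| Model | Arm estimate | SE | p | Baseline coefficient |
|---|---|---|---|---|
| Model 1 (change, unadjusted) | 0.20353 | 0.08695 | 0.0202 | none |
| Model 2 (change + baseline) | 0.20616067 | 0.08277851 | 0.01356631 | −0.353 |
| Endline + baseline | 0.20616067 | 0.08277851 | 0.01356631 | 0.647 |

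Robust (HC1) standard errors also coincide. Only Model 1 differs, and section 5.1 already sets Model 1 beside Model 2. For 2SLS in the same trial, change without baseline gives 0.2841 and endline plus baseline gives 0.2881, so there the comparison can differ. With baseline added to the change-score 2SLS, the two again coincide (0.2881).

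**3. Where the ITT identity can break.** If a section 4 control (say PHQ-9 when SRI is analysed) enters the change-score model but not the endline model, the two estimates can differ. That difference reflects the covariate, not change versus endline.

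**4. What loss could do (illustration).** From the documents: 80 women per city and 2:1 allocation (Protocol), three cities (SAP section 3), so N = 240, or 160:80. Assumed: loss p in each arm (T treatment, C control), a leaver-stayer gap g in SD units after baseline adjustment, a baseline-endline correlation r, a true effect of zero and a two-sided 5% test.

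- Bias if leavers are of the same type in both arms: (pC − pT) × g. If of opposite type: (pC + pT) × g.
- SE = √[(1 − r²)(1/nT + 1/nC)], where n is the number analysed.
- With d = bias/SE, false-positive rate = P(|Z + d| > 1.96).

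| Loss T/C | g | r | Analysed | SE | Same type: bias, d, rate | Opposite type: bias, d, rate |
|---|---|---|---|---|---|---|
| 5%/15% | 0.25 | 0.3 | 152:68 | 0.139 | 0.025, 0.18, 5.4% | 0.05, 0.36, 6.5% |
| 10%/25% | 0.5 | 0.5 | 144:60 | 0.133 | 0.075, 0.56, 8.7% | 0.175, 1.32, 26% |
| 10%/25% | 0.5 | 0.7 | 144:60 | 0.110 | 0.075, 0.68, 10% | 0.175, 1.59, 36% |
| 15%/30% | 0.5 | 0.7 | 136:56 | 0.113 | 0.075, 0.66, 10% | 0.225, 1.98, 51% |

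Example, second row: (0.25 − 0.10) × 0.5 = 0.075; √[0.75 × (1/144 + 1/60)] = 0.133; 0.075/0.133 = 0.56.

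With the protocol's four cities (N = 320, 192:80 analysed), the second-row SE is 0.115 and the ratios are 0.65 and 1.52.

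**5. Two limiting cases.** If loss differs by arm (10%/25%) but is unrelated to outcome, simulated bias is under 0.001 SD and the false-positive rate 4.7%. If loss is equal at 17.5% but leavers are of opposite type, bias is (0.175 + 0.175) × 0.5 = 0.175 SD, which a comparison of retention cannot show.

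**6. Why imputation alone is not enough.** In the second-row scenario, imputing by arm from baseline leaves simulated bias at 0.074-0.076 SD (same type) or 0.177-0.181 SD (opposite). A delta shift equal to the assumed gap brings it below 0.01 SD. This follows from the assumed mechanism and does not show that such loss occurs. The shift in the ITT is pT·dT − pC·dC, where dT and dC are the deltas in each arm. At 10%/25% loss it spans −0.175 to +0.175 SD for deltas between −0.5 and +0.5 SD.

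**The case against.** **The section 7 comparison is redundant, not wrong.** It biases no estimate. Read as Model 1 against baseline-adjusted endline, it is a standard contrast that can differ. This stands, but section 5.1 already provides that contrast. A reader might infer that section 7 is worthless throughout. The documents do not support that, because it remains informative for the 2SLS.

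**The agreement is not unconditional.** Section 4 could put a control on one side only. This stands, so the identity must be stated with its condition of same participants and same covariates.

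**The protocol's mixed model would help.** Fitted by likelihood, it could use partial follow-up under missing at random. However, the SAP specifies OLS on change scores instead, neither document presents the mixed model as a remedy for attrition, and it would not address loss that depends on the unseen outcome.

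**Differential loss is not shown.** HIAS case management also extends to "participants who have been randomly assigned to the control group" (Protocol, Case Management Protocol and Referral Routes). Outcome data are not gathered by programme staff alone: "Data collectors will be hired and trained by Los Andes and the RSRI team members" (Protocol, Data Collection). The documents give no retention figures and no reason to expect opposite types of leaver in the two arms. This stands in full. It limits what can be said about size, but not the finding that the plan could not detect the problem.

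**This is a pilot.** A delta analysis for three outcomes may seem heavy. Yet SAP section 1 sets out to assess impact and to estimate ITT and LATE, and the extra work needs no new data.

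**Conclusion.** The point holds in a conditional form and should be fixed before analysis. For ITT Models 2 and 3, with the same participants and covariates, the section 7 comparison is an identity and gives no robustness evidence. That is algebra and rests on no assumption about the data. The textual gaps are equally clear: no comparison of loss by arm, no consequence of the attrition analysis for any estimate, and no stated role for multiple imputation.

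The size is not established. At N = 240 the assumed ranges (losses 5%/15% to 15%/30%, gaps 0.25-0.5 SD, correlations 0.3-0.7) give 0.18-0.68 SE for same-type leavers and 0.36-1.98 SE for opposite-type leavers. At the low end the false-positive rate is close to nominal; the high opposite-type figures need a pattern for which the documents give no reason.

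A reader might infer that the trial's estimates are biased by attrition, or that imputation alone would repair them. The documents do not support the first, and the second fails if loss depends on the unseen outcome.

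**What to change.** 1. **Section 6.** Report retention by arm and add arm to the logistic model. Treat any arm-by-baseline terms as exploratory: at 10%/25% loss and N = 240 there are only 16 + 20 = 36 losses.
2. **Section 7.** Stop presenting the endline-adjusted model as a robustness check for ITT Models 2 and 3. Keep the comparison for the 2SLS, or add the baseline value to the 2SLS in section 5.2. State that both sides use the same covariates, including any added under section 4.
3. **Replacement ITT check.** Give multiple imputation a role: run it by arm for SRI, PHQ-9 and BRCS, using city and the baseline outcomes, plus 11-month values if that protocol wave is collected. This is the missing-at-random reference. Repeat it with a delta shift varied separately by arm over a stated range, for example −0.5 to +0.5 SD, and report how far both the ITT and the LATE move.

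The cost is SAP wording and a few Stata commands on data already scheduled; multiple imputation is already in the software list. The downside is a little more analysis and possibly wider, less favourable ranges.
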